4.2 Exclusion criteria

- 4.201 Failure to meet any of the criteria set forth in section 4.1.

- 4.202 Significant shunting to the lung (>20%) identified on MAA scan.
- 4.203 Unsuccessful closure of major collateral blood flows from the hepatic artery to non-targeted organs such as the GI tract. Small collaterals that are considered to be safe for Sir-Sphere® treatment by interventional radiologists and radiation oncologists are eligible.
- 4.204 A solitary liver metastasis that is amenable to surgical removal for potential cure.
- 4.205 Presence of symptomatic liver failure including ascites and hepatic encephalopathy.
- 4.206 Presence of life-limiting extra-hepatic metastasis that requires a systemic treatment within 3 months. Patients with extra-hepatic metastasis that can be controlled with a loco-regional treatment are eligible.
- 4.207 Presence of untreated brain metastases. If patients have had previous treatment for brain metastasis, an MRI or CT scan of the brain must confirm the stabilization of the brain metastasis for more than 4 weeks.
- 4.208 Occlusion of the main portal vein, or inadequate collateral flow around an occluded branch of the portal vein as determined by angiography.
- 4.209 Presence of uncontrolled hypertension or congestive heart failure, or acute myocardial infarction within 6 months of entry.
- 4.210 Presence of any other medical complications that imply a survival of less than six months.
- 4.211 Uncontrolled severe bleeding tendency or active GI bleeding.
- 4.212 Significant allergic reaction to iodinated contrast.

- 4.213 Systemic chemotherapy within 2 weeks prior to study entry (signing consent form).
- 4.214 Previous radiation treatment that includes the liver in the main radiation field.
- 4.215 Pregnancy or breast-feeding women.
- 4.216 Biliary obstruction, biliary stent, or prior biliary surgery including sphincterotomy but excluding cholecystectomy.
- 4.217 Previous treatment with isolated hepatic perfusion
- 4.218 Children under the age of 18

5.0 Treatment Schedule

5.1 Pre-study Evaluation

MRI of the abdomen (with and without gadolinium) and CT of the chest, abdomen and pelvis (with and without intravenous contrast). Both imaging exams should be performed prior to enrolling patients to evaluate for extrahepatic disease and tumor burden within the liver. Comprehensive examination including history, physical examination, and laboratory tests to confirm eligibility of patients for the study will also be done (Schedule table). These tests should be done within 4 weeks prior to enrollment of patients to confirm their eligibility. Once their eligibility is confirmed, flow study and radiosphere treatment will be scheduled.

5.2 Flow study (therapy-planning angiography) and pretreatment assessment

Within 4 weeks of radiosphere treatment, therapy planning arteriography of the superior mesenteric and celiac arteries will be performed.

The major purpose of the flow study is as follows:

- 1) Confirm the ability to selectively catheterize the hepatic arterial vasculature.
- 2) Assess the flow characteristics in the hepatic arteries.
- 3) Determine the hepatic arterial supply to the tumor, i.e., right, left or both hepatic arteries.

- 4) Determine the influence of hepatic arterial anatomy relative to the intrahepatic distribution of tumor on the ability to treat the diseased portion of the liver as a single unilobar treatment, or two sequential unilobar treatments, or 2 fractionated whole liver treatments.
- 5) Confirm the absence of significant, uncorrectable blood shunting from the liver to the gastrointestinal tract or other abdominal organs (e.g., pancreas).
- 6) Perform a technetium-99m macro-aggregated albumin (99m Tc-MAA) study to assess the presence and degree of lung shunting of the microspheres from the liver.

During the therapy planning angiography, selective arteriography of the proper, right and left hepatic arteries will be obtained in at least two projections (i.e. PA, RAO) to look for extrahepatic arterial blood supply arising from the hepatic arteries. Coil embolization of extrahepatic arteries (i.e. right gastric, gastroduodenal artery) will be performed as deemed necessary by the interventional radiologist performing the study. Following coil embolization of extrahepatic arteries, 99m Tc-MAA particles will be injected into the proper hepatic artery or injected separately into right and left hepatic arteries by splitting the 99m Tc-MAA dose. The injection location of 99m Tc-MAA will also be at the discretion of the interventional radiologist performing the procedure. The patient will be transported to nuclear medicine for a single photon emission CT (SPECT) scan to assess for shunting to the lungs and extrahepatic activity. CT scan of chest, abdomen, and pelvis with and without contrast, MRI of the abdomen with and without gadolinium, and PET scan will be performed as baseline imaging tests for radiosphere treatment. These tests will be done within 4 weeks of radiosphere treatment.

The dose for treatment will be determined by the radiation oncology attending using the MRI and/or CT scan imaging and the results of flow study using the equations described in Section 9. The determined dose will be ordered.

5.3 Biopsy of hepatic metastasis

Within 4 weeks of radiosphere treatment, tumor specimens will be obtained by core biopsy of a representative hepatic metastasis. DNA as well as RNA will be extracted from the core biopsy specimens after confirming diagnosis of metastatic melanoma by histology and will be used for molecular studies including DNA array analysis and genome-wide SNP analysis. If patients have established diagnosis of metastatic uveal melanoma to the liver, they could decline this biopsy.

The tumor biopsy will also be exempt if the tumor tissue specimen can not be obtained by a conventional technique such as US-guided or CT-guided biopsy.

5.4 Radioactive microsphere treatment

Within 4 weeks after the flow study, selective internal radiation therapy (SIRT) using yttrium-90 SIR-Spheres® microspheres (radiosphere treatment) will be performed. Due to multiple, bilobar metastases, both right and left hepatic lobes need to be treated in the majority of patients. The goal of therapy is to treat the tumor bearing liver in 2 sessions. Treatments are preferentially done in a lobar fashion. In the setting of complex anatomy, fractionated whole liver therapy is used as an alternative. In general, the delivery of radioactive microspheres will require two sequential unilobar treatments separated by a period of 4 ± 1 weeks. The lobe to be treated first will be determined by the treating physicians. The radiosphere dose for each hepatic lobe will be determined based on the tumor volume in individual lobes.

In patients whose hepatic artery does not allow two separate sequential unilobar treatments, whole liver treatment via the proper hepatic artery may be performed if no extrahepatic arteries are identified distal to the catheter site intended for radioactive microsphere delivery. The dose will be delivered in two fractionated doses separated by 4 ± 1 weeks (fractionated whole liver).

If a prior hepatectomy has been performed leaving a single lobe for treatment, or if metastatic disease is confined to a single lobe, the entire dose will be delivered in a single session to the affected lobe.

Treatment will be administered on an outpatient basis with overnight, 23-hour observation permitted at the investigator's discretion. Patients will receive the supportive care as described in Section 7.

Approximately 100ml of blood specimens will be obtained for Peripheral Blood Mononuclear Cell (PBMC) collection prior to radiosphere treatment. Additionally, 10 ml of blood specimens will be obtained for serum collection prior to, and 1 hour after radiosphere treatment.

Blood tests including CBC with differential, comprehensive metabolic panel including total

bilirubin, SGOT (AST), SGPT (ALT), LDH, alkaline phosphatase, albumin, creatinine, BUN, glucose, calcium, and LDH will be ordered every 2 weeks for one month, then every month for three months to monitor treatment-related toxicity.

5.5 One-month post-procedure visit

In 4 weeks (\pm 1 week) after the last radiosphere treatment (usually after the second radiosphere treatment), patients will be evaluated for treatment-related acute toxicity. Patient will also have a 1-month follow-up CT scan of the chest, abdomen and pelvis (with and without contrast) to assess extrahepatic disease.

Approximately 100ml of blood specimens will be obtained for PBMC collection. Additionally, 10 ml of blood specimens will be obtained for serum collection.

5.6 3-month post-procedure visit

Three months (\pm 2 weeks) after the last radiosphere treatment (usually after the second radiosphere treatment), patients will be evaluated for response to treatment and late toxicity. CT scan of the chest, abdomen and pelvis (with and without contrast); MRI of the abdomen (with and without gadolinium) and PET scan will be obtained.

Approximately 100ml of blood specimens will be obtained for PBMC collection. Additionally, 10 ml of blood specimens will be obtained for serum collection.

5.7 Subsequent follow-up visits

After the 3-month office visit, patients will be followed every three months for the maximum of two years. CT scan of the chest, abdomen and pelvis (with and without contrast); MRI of the abdomen (with and without gadolinium), PET scan, and blood test including CBC with differential, comprehensive metabolic panel including total bilirubin, SGOT (AST), SGPT (ALT), LDH, alkaline phosphatase, albumin, creatinine, BUN, glucose, and calcium will be obtained prior to the individual follow-up visits.

5.8 End of study visit

At the conclusion of two-year follow-up or upon withdrawal of patients from the study, patients will be evaluated by a study physician. CT scan of the chest, abdomen and pelvis (with and without contrast); MRI of the abdomen (with and without gadolinium), PET scan, and blood test including CBC with differential, comprehensive metabolic panel including total bilirubin, SGOT (AST), SGPT (ALT), LDH, alkaline phosphatase, albumin, creatinine, BUN, glucose, and calcium will be ordered. If patients are evaluated with the above tests within 1 month prior to the conclusion of study, this visit will be substituted for the end of study visit.

5.9 Withdrawal of subjects

The following criteria will be used to withdraw patients from the study.

1. Progressive disease (PD) by RECIST criteria or at the end of 2 years following treatment initiation. Patients will be withdrawn from the study if significant extra-hepatic disease develops and systemic therapy is required. In addition, if patients demonstrate significant intra-hepatic tumor progression and require additional percutaneous or catheter-directed therapy, they will be withdrawn from the study.
2. Unacceptable toxicity. This is defined as greater than or equal to grade 4 toxicity.
3. The patient may withdraw from the study at any time for any reason with written notification to the investigator.
4. Investigator's decision that it is in the patient's best interest to come off study.
5. A major protocol violation, or if requested by the sponsor or regulatory agency.
6. The withdrawal of a subject from the trial may also occur if the subject is noncompliant. This will not affect the standard of the patient's future medical care.
7. Death of a subject. **If a subject dies while participating in this study, regardless of the cause, an SAE form must be completed.**

5.10 Follow-up after withdrawal from study

All patients, including patients who discontinue protocol therapy because of toxicity or progressive disease must be followed every three months up to a minimum of 2 years to determine clinical status and to document time to progression and duration of survival. Telephone contact and record review is allowed for this purpose. If patients are removed from study due to grade 4 toxicity, patients must be followed until toxicity level decreases to \leq grade 1 or considered resolved with sequelae.

For patients who achieved PR, CR, or SD in the liver metastases after radiosphere treatment, tumor measurements should be continued every 3 months for up to 2 years after initiation of protocol therapy or until PD in the liver metastases is confirmed.

6.0 Supportive Care Guidelines

6.1 Post-Treatment Care

Following treatment, the patient will remain under observation according to standard care guidelines for the aftercare of procedures involving femoral artery catheterization. This typically involves at least 6-hour monitoring. After 6 hours of observation, the patient will be sent home when the interventional radiology (IR) attending physician determines that the patient is stable and that there is no risk of bleeding from the catheter site. Patients could be kept over night for further observation at the discretion of IR attending or study physicians. At the time of discharge, patients will be instructed regarding aftercare and will be provided with a 24-hour telephone number that they may use to contact the IR attending or study physician if they develop a problem.

6.2 Pre- and Post-treatment Supportive Therapies

The following supportive therapy will be administered at the discretion of investigator, unless otherwise contraindicated:

- (1) Pre- and post-therapy intravenous hydration.
- (2) Gastrointestinal prophylaxis to prevent GI inflammation and ulceration: a proton pump inhibitor (e.g. Pantoprazole 40mg orally once daily) continuing for 4 weeks post treatment.
- (3) Anti-nausea prophylaxis: e.g., anti-emetics (e.g. Ondansetron 8mg orally or i.v., every 8 hours, PRN) for post-treatment nausea.
- (4) Post-embolization syndrome prophylaxis: Provided the patient is not diabetic – and oral steroids are not otherwise contraindicated – a tapering dose of oral corticosteroids (e.g., Methylprednisolone 24mg, 20mg, 16mg, 12mg, 8mg, 4mg orally on days 0, 1, 2, 3, 4 & 5 respectively, or dexamethazone 4 mg, bid for 3 days, then once a day for 3 days) commencing on the day of treatment will be administered.
- (5) Pain control: Oral analgesia (e.g., Ketorolac 10mg orally every 6 hours PRN, or oxycodone 5 mg, orally every 4 hours PRN) may be required for 1 week following treatment to relieve pain from radiation injury and embolic effects related to SIR-Spheres® microspheres, and liver capsular pain from tumor edema.

7.0 Evaluation of Response

7.1 Evaluation of clinical response

7.1.1 Definition of Measurable Disease

Measurable disease

Measurable disease is defined by the presence of at least one measurable lesion as defined below and adapted from the RECIST criteria version 1.1 (34). All measurements must be recorded in metric notation. If measurable disease is restricted to a solitary lesion, its malignant nature should previously have been confirmed by cytology/histology.

Since some melanoma metastases contain melanin pigment and since successfully treated liver metastases may develop significant necrosis, evaluation of radiological response after embolization treatments is generally difficult. Therefore, we will obtain CT scan and MRI of the liver, and PET scan of the body for the precise evaluation of radiological responses. However, the same modality will be used for measurement of the liver metastases and assessment of the response. We prefer to use MRI for response assessment due to its superiority in measurement of tumor size and assessment of tumor necrosis compared to traditional spiral CT scans.

The longest diameter (LD) of the largest liver lesion should be ≥ 10 mm by spiral CT scan or MRI in order to become eligible for the study.

Non-measurable disease

All other lesions including small lesions (<10 mm on spiral CT scans or MRI) are considered “non-measurable”. The following lesions are also considered as “non-measurable”: Bone lesions, leptomeningeal disease, ascites, pleural/pericardial effusion, abdominal masses that are not confirmed and followed by imaging techniques, tumors treated by irradiation or by intra-tumor injection therapy.

7.1.2 Baseline Documentation of "Target" and "Non-Target" Lesions

Target Lesions (Indicator Lesions)

The target lesions are defined as measurable lesions that will be used for evaluation of response. For this protocol, target liver lesions require serial measurement of a longest diameter and should be ≥ 10 mm by spiral CT scan or MRI at the time of study entry.

Target lesions (up to a maximum number of 5 for the liver metastases) must be identified and measured at baseline prior to the initiation of radiosphere treatment. Target lesions must be selected on the basis of their size (LD) and suitability for repetitive measurements.

Non-Target Lesions

All other lesions (or sites of melanoma) must be identified as “non-target” and their location and characteristics must be recorded at baseline. During follow-up evaluations, these lesions must be followed as “present” or “absent”.

7.1.3 Evaluation of overall response in the liver metastases

Clinical response in the liver metastases will be evaluated 3 months after the last radiosphere treatment using CT scans or MRI of the abdomen. The same modality must be used for serial measurements of target lesions. The sum of the longest diameter (LD) of up to 5 target liver lesions will be used to determine response. The investigators must identify target indicator lesions and measure them within 4 weeks prior to the first radiosphere treatment as baseline. The investigators will then measure the same target lesions 3 months after the last radiosphere treatment.

The sum of the baseline LDs will be compared to the sum of LDs after radiosphere treatments. New lesions will be defined as lesions that appear in the treated lobe(s) of the liver after the baseline evaluation and should be ≥ 10 mm in longest diameter. Development of new lesion(s) in an untreated lobe (area) of the liver **will not** be considered as “Progressive Disease” for evaluation of liver response.

7.1.4 Response criteria for liver metastases

The response of liver metastases will be evaluated by MRI or CT scans using the criteria adapted from the international criteria proposed by the Response Evaluation Criteria in Solid Tumors (RECIST) Committee. The same imaging modality must be used for the serial measurements of

tumor diameter. The response must be confirmed by two consecutive imaging tests performed not less than 4 weeks apart. The definition of response of liver metastases in the treated lobe(s) is shown in Table 1. Evaluation of target and non-target lesions in the treated liver lobe(s) to determine response of liver metastases is shown in Table 2.

In terms of PET scan assessment, up to 6 metabolically active metastases with SUV of 2 or greater will be recorded prior to the radiosphere treatment. If more than 50% of these lesions show SUV of 2 or less at 3 month PET assessment, the radiosphere treatment will be considered to be “effective” (35).

Table 1. The definition of response of liver metastases in the treated lobe(s)

Complete Response (CR)	Disappearance of all target and non-target liver lesions
Partial Response (PR)	$\geq 30\%$ decrease in the sum of the longest diameters (“sum LD”) relative to baseline sum LD with at least stable non-target liver lesions
Stable Disease (SD)	Absence of change which would qualify as response or progression
Progression (PD)	$\geq 20\%$ increase in the sum LD in target liver lesions or unequivocal progression of non-target liver lesions in the treated lobe(s) Appearance of one or more new liver lesions ≥ 10 mm in the treated lobe(s)

To be assigned a status of CR or PR, changes in tumor measurements must be confirmed by the follow-up assessment using the same imaging test at a minimum interval of 4 weeks. The patients who have a CR or PR without confirmatory assessment will be categorized as SD. In the case of SD, follow-up measurements must have met the SD criteria at least once at a minimum interval of 4 weeks. The patients who have a SD without confirmatory assessment will be categorized as PD.

Table 2. Evaluation of target and non-target lesions in the treated liver lobe(s)

Target Liver Lesions	Non-Target Liver Lesions	New Liver Lesions in the treated lobes	Overall Liver Response
CR	CR	No	CR
CR	SD	No	PR
PR	Non-PD	No	PR
SD	Non-PD	No	SD
PD	Any	Yes or No	PD
Any	PD	Yes or No	PD
Any	Any	Yes	PD

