4.0 Selection of Patients

4.1 Inclusion criteria

- 4.11 Histologically confirmed metastatic uveal melanoma in the liver. Patients must have at least one untreated, or progressed liver metastasis that is ≥ 10 mm in longest diameter by spiral CT scan or MRI. The total volume of the tumors must be less than 50% of the liver volume.
- 4.12 Either no previous trans-hepatic arterial treatment or progressive hepatic metastasis after prior regional treatment with trans-arterial embolization. Embolization of hepatic artery with different types of medication will be considered to be one regional treatment.
- 4.13 Willingness and ability to give informed consent.
- 4.14 ECOG performance status of 0, or 1.
- 4.14 Adequate renal and bone marrow functions:
Serum creatinine ≤ 2.0 mg/dl, granulocyte count $\geq 1000/\text{mm}^3$, and platelet count $\geq 100,000/\text{mm}^3$.
- 4.15 Adequate liver function: total bilirubin <1.6 mg/ml and albumin > 3.0 g/dl,

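### Target-lesion progression in Table 1 has no minimum millimetre increase, so with one 10 mm target lesion a 2 mm reading difference can turn a stable patient into a primary endpoint failure

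*Combined protocol and SAP*

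**What the plan says.** **Progression rule.** Table 1 in section 7.1.4 defines target-lesion PD as a 20% or greater "increase in the sum LD in target liver lesions or unequivocal progression of non-target liver lesions in the treated lobe(s". The comparison is with baseline (7.1.3): "The sum of the baseline LDs will be compared to the sum of LDs after radiosphere treatments". The only millimetre figure in the PD row is the 10 mm size needed for a new lesion to count.

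**Smallest disease allowed.** Inclusion criterion 4.11 states: "Patients must have at least one untreated, or progressed liver metastasis that is ≥ 10 mm in longest diameter". Section 7.1.2 accepts target lesions from 10 mm. Section 7.1.1 foresees a single measurable lesion: "If measurable disease is restricted to a solitary lesion, its malignant nature should previously have been confirmed by cytology/histology". Up to five lesions enter the sum (7.1.3).

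**Confirmation.** Section 7.1.4 says: "To be assigned a status of CR or PR, changes in tumor measurements must be confirmed", at an interval of at least 4 weeks. SD must also be met again at that interval, and unconfirmed SD becomes PD. No such rule is written for PD, and Table 2 maps target-lesion PD directly to overall PD. Section 5.10 (continued measurement) and section 7.2 (PFS-L) speak of progression being confirmed, but give no repeat scan or interval.

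**Use.** Section 12.0 makes CR+PR+SD the primary endpoint and tests it in each group with stopping limits of 3/8 and 10/24.

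**The concern.** A purely proportional threshold shrinks with the lesion. At the entry minimum it is 2 mm, which may be no larger than the difference between two readings of an unchanged lesion. Section 7.1.1 itself says that radiological response is hard to judge after embolization because of pigment and necrosis.

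For a truly stable patient this error works in one direction: it can only move the patient from success to failure. It therefore lowers the observed clinical benefit rate, raises the chance of a wrong stop after eight patients, and reduces power. The confirmation rule for SD adds to the exposure if a stable patient must stay below the threshold on a second scan too.

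**Working it through.** **1. The plan's own figures.** Inputs from section 12.0: 30% and 60%, stop at 3 or fewer of 8, ineffective at 10 or fewer of 24. For benefit rate p, the probability of declaring activity is the sum over x = 4 to 8 of P(X₁ = x) × P(X₂ ≥ 11 − x), with X₁ ~ Bin(8, p) and X₂ ~ Bin(16, p).
- p = 0.60: 0.806, with early stop 0.174. This reproduces the stated 80.6% and 0.17.
- p = 0.30: 0.046, with early stop 0.806. This agrees with the stated 5% limit and 0.81.

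**2. Threshold in millimetres** (0.20 × baseline sum; no assumption needed).

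| Baseline sum | Increase scored as PD |
|---|---|
| 10 mm | 2 mm |
| 15 mm | 3 mm |
| 20 mm | 4 mm |
| 25 mm | 5 mm |
| 50 mm | 10 mm |

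A 5 mm minimum would alter the rule only for baseline sums below 25 mm.

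**3. False PD in an unchanged single lesion.** The documents give no measurement error. Assume independent normal reading error with SD σ of 0.5 to 1.5 mm, at baseline as well as follow-up. PD is called if follow-up ≥ 1.2 × baseline, so for true size B the single-scan rate is 1 − Φ(0.2B / (σ√(1 + 1.2²))). For B = 10 and σ = 1 this is 1 − Φ(2/1.562) = 0.100. The either-of-two-scans rates come from simulation (1,000,000 draws).

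| Lesion | σ | One scan | Either of two scans | One scan, with 5 mm minimum |
|---|---|---|---|---|
| 10 mm | 0.5 | 0.5% | 1.0% | about 0 |
| 10 mm | 1.0 | 10% | 16% | 0.02% |
| 10 mm | 1.5 | 20% | 30% | 0.9% |
| 15 mm | 1.0 | 2.7% | 4.8% | 0.02% |
| 15 mm | 1.5 | 10% | 16% | 0.9% |
| 20 mm | 1.0 | 0.5% | 1.0% | 0.02% |
| 20 mm | 1.5 | 4.4% | 7.5% | 0.9% |

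For two 10 mm lesions at σ = 1.0 to 1.5, the either-of-two rate is 6% to 18% now and 1% to 8% with a 5 mm minimum.

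**4. Effect on power.** Let s be the share of patients with small sums and l the fraction of their stabilizations lost. The observed rate is 0.60 × (1 − s × l). Both s and l are assumptions.

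| s | l | Observed rate | Power | Early stop |
|---|---|---|---|---|
| 10% | 5% | 0.597 | 80.0% | 0.18 |
| 10% | 10% | 0.594 | 79.4% | 0.18 |
| 25% | 5% | 0.5925 | 79.1% | 0.19 |
| 25% | 10% | 0.585 | 77.6% | 0.20 |
| 25% | 16% | 0.576 | 75.6% | 0.21 |
| 25% | 30% | 0.555 | 70.5% | 0.25 |

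The last two rows give every small-sum patient the rate for a single 10 mm lesion on either of two scans, so they are an upper case.

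**5. Type I error.** The same misreading also lowers a true 30% rate. At s = 25% and l = 10% it becomes 0.30 × 0.975 = 0.2925, and type I error is 3.9% instead of 4.6%.

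**6. What a 5 mm minimum would miss.** True growth from 10 to 14 mm, σ = 1, one scan:
- Now: Φ((14 − 12)/1.562) = 0.90.
- With the minimum: Φ((4 − 5)/√2) = 0.24.

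**The case against.** **Small sums are a corner case.** Section 5.4 says most patients need both lobes treated because of multiple, bilobar disease. Section 7.1.2 selects up to five targets by size, and 4.204 excludes a resectable solitary metastasis. This stands: it limits the size of the effect, though the plan still admits the case.

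**Confirmation is not wholly absent.** A reader might infer that PD is never confirmed, so that one noisy reading is irrevocably a PFS-L event and a withdrawal. The documents do not support that. A general sentence in 7.1.4 asks for response to be confirmed on two consecutive scans, 5.10 and 7.2 refer to confirmed progression, and 5.9 withdraws on PD by RECIST rather than by Table 1. What remains is that confirmation of PD is mentioned but never specified, and that the rules written out in 7.1.4 leave it out.

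**The 10 mm new-lesion limit is not a contradiction.** It matches the measurability limit in 7.1.1, so little should be made of the contrast with a 2 mm change.

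**The 30% and 60% may be rates as scored.** Section 12.0 does not say that they are free of misreading. If they already include it, subtracting it again double counts. This is a fair reason to treat the power figures as illustrations.

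**The present bias is conservative, and a minimum is not free.** In an uncontrolled trial where SD is a success, a looser PD rule makes success easier. Suppose 25% of patients have small sums and 16% to 30% of their true failures are relabelled. A true 30% then reads 0.30 + 0.70 × 0.25 × (0.16 to 0.30) = 0.328 to 0.3525, and type I error becomes 8% to 12%. That too is an upper case, since progression through new or non-target lesions, or through larger growth, would still be caught. The direction of the argument stands and belongs in the fix.

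**Conclusion.** The gap is real and its arithmetic needs no assumption: at the smallest disease the plan admits, 2 mm decides the primary endpoint. It should be closed, but it is a modest problem.

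The false-PD rate for an unchanged 10 mm lesion runs from 0.5% to 20% on one scan, and from 1% to 30% if either of two scans counts. That spread reflects the assumed SD of 0.5 to 1.5 mm. The effect is confined to baseline sums below 25 mm, whose share the documents do not give. With a 10% to 25% share and 5% to 10% of stabilizations lost, power is about 78% to 80% instead of 80.6%. A reader might infer a fall to 71% to 76%, but that needs the worst rate for every small-sum patient. The present rule does not inflate type I error. The harm is some lost power and some stable patients wrongly scored as failures.

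**What to change.** 1. In Table 1, require for target-lesion PD both a 20% or greater increase and a minimum absolute increase in sum LD. The documents contain no such figure; 5 mm is an example. Use the same measurement rule for PFS-L in 7.2.
2. Reconcile the wording on confirmed progression in 5.10 and 7.2 with Table 1, stating whether a repeat scan is needed to score PD and at what interval.
3. Report the clinical benefit rate under the 20%-only rule as a sensitivity analysis.

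**Cost.** The change takes one clause in Table 1, matching edits in 5.10 and 7.2, and one extra tabulation. The minimum itself needs no additional scan. With 5 mm nothing changes for baseline sums of 25 mm or more. The downside should be stated in the plan: true growth of a very small single lesion can be scored SD, a success, at the 3-month assessment. For 10 to 14 mm growth at an assumed SD of 1 mm, one-scan detection falls from about 90% to about 24%. The sensitivity analysis shows whether the conclusion depends on such patients.
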